The objectives of this pilot randomized controlled trial are to (1) determine the feasibility and acceptability of study procedures (recruitment, randomization, and data and sample collection) and CSM-IBD; (2) compare CSM-IBD to usual care on changes from baseline to 3 months post intervention in quality of life and daily symptoms (fatigue, sleep disturbance, psychological distress, gastrointestinal symptoms) among IBD patients and (3) explore the association of socioecological factors (age, sex, race, ethnicity, or diet), clinical phenotype (medications, disease distribution, and disease activity), and biological signatures (microbiome and calprotectin) with symptoms at baseline and response to intervention (post intervention).

Methods

Study Design

The proposed study is a 2-arm pilot randomized controlled trial that follows the Consolidated Standards of Reporting Trials and Standard Protocol Items: Recommendations for Interventional Trials guidelines [30,31]. In a 2:1 ratio, 54 participants will be randomized (intervention=36 participants; usual care=18 participants). This randomization scheme was selected to maximize data collection and information regarding the intervention group. The intervention will take place over 8 sessions. The participants will be blinded to the study hypotheses. Web-based self-reported questionnaires will be used to reduce detection bias.

Theoretical Framework

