All procedures will occur remotely; data collection will occur digitally through REDCap (Research Electronic Data Capture; Vanderbilt University), a secure Health Insurance Portability and Accountability Act (HIPAA)-compliant database [52,53]. Individuals meeting eligibility criteria and interested in the study will be asked to sign a consent form and HIPAA form prior to participating in the study. All participants will complete baseline questionnaires (socioecological factors and disease information). Participants will collect a stool sample at home using a stool sample collection kit (instructions and researcher contact information will be provided); a 3-day food record will be collected starting 2 days before the stool sample collection. The stool samples will be placed in home freezers and returned to the School of Nursing Biobehavioral Laboratory. Participants will be provided with ice packs, a Styrofoam mailing box, and return labels. Stool samples will be stored at -80°C until batch processing.

Following baseline data collection, participants will be randomly assigned to the 8-session CSM-IBD or usual care. Immediately post intervention, participants will complete questionnaires, collect a stool sample, and report a 3-day food record. Three months post intervention, participants will complete questionnaires and participate in a qualitative data collection interview. In addition, participants will report whether or not they are continuing the self-management skills learned in the intervention. Semistructured interviews will be conducted to understand the participants' perspective on procedural burden and suggestions to improve the intervention, including satisfaction with the intervention. Interviews will be recorded and transcribed. Participants will be compensated for each assessment completed (baseline, immediately post intervention, and 3 months post intervention). To increase retention, participants in the usual care group will be provided access to the intervention upon study completion. Participants can continue the study despite not completing all data collection assessments and all intervention sessions.

Sample Size

Based on recommendations for preliminary studies [54], we aim for data on 54 participants (36 intervention and 18 usual care). The sample size is appropriate for assessing feasibility and acceptability (aim 1). For aim 2, we will be able to detect fairly large effect sizes of 0.81 with

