80% power. For aim 3, there will be 80% power to detect a correlation of 0.45. As a pilot study, the project is not powered to detect differences or correlations unless they are large.

Recruitment

Overview

Participant recruitment will take place at the UW Inflammatory Bowel Disease Clinics. The UW sees a large number of patients with IBD and serves as a tertiary care clinic for patients with IBD in the Washington, Oregon, Alaska, Montana, and Idaho regions. Recruitment may occur in three different settings: (1) in a clinic, (2) virtually (via telephone, email, or mail), and (3) by posting on the Institute of Translational Health Sciences website. All individuals will be informed that participating or not participating will not influence the care that they receive.

In a Clinic

Weekly prescreening will occur to determine if participants with scheduled IBD clinic appointments may be eligible for the study. The goal of prescreening is to enable purposeful sampling of patients based on demographic (eg, age and race) and disease characteristics (eg, disease activity). Individuals who are eligible will receive a flyer containing the study purpose and contact information from either their health care provider or study staff (depending on feasibility and current COVID-19 restrictions). Individuals will have time to review the study information. Participants can call study staff or complete a REDCap survey to express their interest and complete screening questions.

Virtually

The team may contact potential participants via phone, email, or mail if in-person recruitment becomes difficult or not feasible. All contact will follow the UW's institutional review board guidelines for cold contact recruitment. Those expressing interest in the study will call study staff for more information and then complete additional screening questions.

Institute of Translational Health Sciences Website

Information regarding the study will be posted on the UW Institute of Translational Health Sciences website. Interested individuals can complete the contact form to be contacted by study staff and can complete screening questions digitally.

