Data from the 2 follow-up time points (immediate and 3 months post intervention) will be analyzed together using linear mixed models for each of the outcomes. For example, one model will have a change in the quality of life from baseline to immediate and 3 months post intervention as the outcomes, subject as a random effect, time (immediate or 3 months) as a within-subject fixed factor, and treatment group as an across-subject fixed factor. Baseline quality of life will be included as a covariate in the model, as will any baseline variables that differ between the 2 treatment groups. The parameter for the treatment group factor will provide an estimate of the treatment effect, that is, the difference between the treatment groups in mean change in the quality of life, and a 95% CI on the estimated difference will be computed. We hypothesize participants in the CSM-IBD will report a greater reduction in symptoms compared to those in usual care. A second model will also include an interaction between group and time to test whether the treatment effect is different at the 2 post intervention times. Additional analyses will estimate treatment effects separately for men and women.

Secondary Outcomes

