Analyses of microbiome data will use 3 summary measures—Shannon diversity, richness, and *Firmicutes/Bacteroidetes* ratio—as well as the relative abundance of bacterial families (eg, family Ruminococcaceae) and genera and will control for the read count. For diet, we will focus on protein and fiber intake, as our previous work has indicated these may be important dietary intake components related to the gut microbiome. First, we will examine the associations between socioecological, clinical phenotype, and biological signatures with symptoms at baseline in the total sample using Pearson correlation or Spearman rank correlation based on measure distributions. Scatter plots will be used to visually display these associations. Second, we will examine associations between socioecological, clinical phenotypes, and biological signatures at baseline and response to intervention in the intervention group. Response to intervention is conceptualized as an increase of 8 points on the SIBDQ scale (quality of life) [40] or a 50% decrease from baseline in the GI symptom score [27]. Among the intervention group, we will use the *t* test and chi-square test to compare socioecological factors, clinical phenotypes, and biological signatures among patients with and without a response to treatment.

Monitoring

This study has been classified as a minimal-risk study. The principal investigator has the responsibility for study oversight, including patient safety and data quality, as well as submitting reports to the funder and the institutional review board. Due to the low-risk nature of the CSM-IBD, we do not anticipate any adverse events or serious adverse events. The data safety and monitoring team will meet quarterly to review the study. The team will monitor accrual, withdrawals, data quality, timeliness of data submission, protocol compliance, and the types and frequency of adverse events and serious adverse events. No interim analysis or stopping rules are currently planned. However, if any adverse events or serious adverse events are reported, the data safety and monitoring team will meet within a week to discuss the event and any potential changes needed to the study procedures.

Ethics and Dissemination

Data Management

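### The predictor-of-response analysis fixes t and chi-square tests for every variable, dropping the distribution rule used at baseline, and the r = 0.45 power statement does not say which analysis it covers (minor)

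*Combined protocol and SAP*

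**What the plan says.** Under Statistical Analysis, Secondary Outcomes, aim 3 has two analyses.

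- **Baseline associations, total sample.** Factors are related to symptoms "using Pearson correlation or Spearman rank correlation based on measure distributions".
- **Predictors of response, intervention group only.** Response is made binary: "Response to intervention is conceptualized as an increase of 8 points on the SIBDQ scale (quality of life"), or a halving of the GI symptom score. Responders and non-responders are then compared by the t "test and chi-square test to compare socioecological factors, clinical phenotypes, and biological signatures among patients with and without a response to treatment". No rank test, transformation, exact test or rule for merging categories is given.

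The group sizes come from Study Design: "In a 2:1 ratio, 54 participants will be randomized (intervention=36 participants; usual care=18 participants"). Sample Size gives one power statement for this aim: "For aim 3, there will be 80% power to detect a correlation of 0.45". It names no n, alpha or analysis. The same section adds that the pilot has power only for large effects.

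**The concern.** The same baseline variables appear in both analyses. The first treats their distribution as an open question; the second does not. Two of the biological measures, fecal calprotectin and the relative abundance of families and genera, are candidates for strong right skew. Several other predictors are categorical with multiple levels: race or ethnicity, education, employment, partner status, medications and Montreal distribution. With 36 people divided by response, some cells will be small.

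The power statement adds to this. A correlation is quoted, but the analysis in the intervention group is written as a group comparison after a responder split. A reader cannot tell what size of association that analysis can detect. Predictors of response are half of the third objective, and the findings are meant to shape a full-scale trial, so a real predictor could be set aside for lack of power.

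**Working it through.** **Inputs.** From the documents: 54 in total, 36 and 18 by arm; 80% power at r = 0.45; the tests quoted above. Assumed, because the documents do not give them: two-sided alpha 0.05 (consistent with "a 95% CI on the estimated difference will be computed" in the primary analysis), 20-50% responders, log-normal skewed predictors, category prevalences, and no dropout.

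**1. Reproduce the plan's figures.** The aim 2 figure checks the assumed alpha: (1.960 + 0.842) × √(1/36 + 1/18) = 2.802 × 0.2887 = 0.81, as stated. For aim 3, the smallest detectable correlation is tanh(2.802/√(n − 3)):

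- n = 36: tanh(2.802/√33) = 0.452; power at r = 0.45 is 79.5%.
- n = 54: tanh(2.802/√51) = 0.373; power at r = 0.45 is 93%.

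So 0.45 is the figure for a correlation in the intervention group. The baseline correlations in the total sample do better than stated.

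**2. What the responder split does to 0.45.** A pooled t test is the test of the point-biserial correlation between predictor and responder status. The differences detectable with 80% power (noncentral t), converted by r = d/√(d² + n²/(n₁n₂)), are:

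| Responders v non-responders | Detectable d (SD) | Point-biserial r |
|---|---|---|
| 18 v 18 | 0.96 | 0.43 |
| 14 v 22 | 0.99 | 0.43 |
| 11 v 25 | 1.04 | 0.43 |
| 7 v 29 | 1.21 | 0.43 |

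If 0.45 is the correlation with responder status, the t test therefore has about 80% power or slightly more. If 0.45 is the correlation with continuous response, the split shrinks it by φ(z)/√(q(1 − q)), where q is the responder share and φ(z) the normal density at the cut. It becomes 0.45 × 0.399/0.5 = 0.36 at q = 50% and 0.45 × 0.280/0.4 = 0.315 at q = 20%. Simulated t-test power is then about 59% at 50% responders, falling to about 48% at 20%; separate runs differ by about a point.

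**3. Skewed predictors.** Simulation with 14 responders v 22 non-responders, log-normal predictor, responders higher by 1 SD on the log scale:

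| Log SD | Raw t test | Rank-sum | Log-scale t test |
|---|---|---|---|
| 0.5 | 79% | 78-80% | 81-82% |
| 0.75 | 76% | 78-80% | 81-82% |
| 1.0 | 68% | 78-80% | 81-82% |
| 1.5 | 56% | 78-80% | 81-82% |

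With no true difference, the pooled t test rejected in 2.7-5.4% of runs (log SD 1.0 and 1.5; 18, 11 or 7 responders).

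**4. Sparse categories.** The smallest expected count is 36 × category share × smaller response share. For a 20% category and 40% responders it is 36 × 0.20 × 0.40 = 2.9. To reach 5, a category must hold at least 5/(36 × 0.5) = 28% of the group (10 people) at a 50/50 split, or 5/(36 × 0.3) = 46% at 30/70.

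**The case against.** The strongest reply concerns power. A reader might infer that the design does not deliver its stated power, or that 0.45 belongs to neither planned analysis. The documents do not support that. Sample Size does not say which correlation is meant, and on the responder-status reading the t test in 36 people does reach about 80%. The drop to 48-59% depends on the other reading. What can be said is that the statement is incomplete.

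A reader might also infer that the t test is invalid for these data. It is not: its false-positive rate stayed near or below 5%. Nor is the loss of power certain. It is negligible at log SD 0.5, the documents give no SDs, and predictors such as age, Shannon diversity or fiber intake need not be heavily skewed. The sparse-cell figures likewise rest on assumed prevalences.

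The responder definition is referenced and evidently deliberate. Replacing it with continuous change would alter the question and drop the GI symptom criterion, so that is a matter of judgement and not a correction. Finally, the aim is exploratory, the plan admits that only large effects are detectable, Future Directions leaves predictors to later research, and no primary conclusion rests on these tests.

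All of this stands and limits the severity. It does not explain why the distribution rule stops at baseline, or why no exact test is allowed for.

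**Conclusion.** The point holds as a minor one, with two parts.

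- **Choice of test.** The plan omits, for the response analysis, the allowance for non-normal measures that it makes at baseline, and it has no provision for sparse tables. The cost is power: roughly 10 percentage points at log SD 1.0 (68% v 78-80%) and over 20 at log SD 1.5 (56% v 78-80%), and close to none under mild skew. Any category held by fewer than 10 of the 36 gives an expected count below 5 even at an even responder split.
- **Power statement.** The 0.45 reproduces for a correlation with n = 36 and two-sided 0.05. It is conservative for the baseline correlations (0.37 at n = 54). For the response analysis it holds if it refers to responder status; otherwise power is about 48-59%. The plan should say which is meant.

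The documents support neither a claim that the t test is wrong nor a claim that the stated power is false.

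**What to change.** In Statistical Analysis, Secondary Outcomes:

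- Apply the baseline distribution rule to the response comparison: a rank-sum test or log-scale t test for skewed measures.
- Use Fisher's exact test where any expected count is below 5.
- Keep the responder comparison as defined, and add a baseline-adjusted analysis of continuous SIBDQ change against each predictor. Use regression in general, and partial Spearman correlation only for ordered or continuous predictors, since it does not suit nominal ones such as race or medication.

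In Sample Size, restate aim 3 power with n, alpha and analysis: about r = 0.37 for the baseline correlations (n = 54) and about r = 0.45 for a correlation in the intervention group (n = 36), both before dropout. Add that after the responder split the t test detects a difference of about 0.96-1.21 SD, depending on the responder share. Adjusting for baseline changes the 0.45 little: tanh(2.802/√32) = 0.458. Dropout matters more: with 32 or 29 evaluable people (an assumption) the unadjusted figure becomes tanh(2.802/√29) = 0.48 or tanh(2.802/√26) = 0.50.

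The cost is a few sentences and slightly more analysis for an exploratory aim. No new data are needed, because SIBDQ change with baseline as a covariate is already modelled under Primary Outcomes.
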